7.3.1 Primary endpoint analyses

For each comparison between test and reference treatment, the statistical model used will be an ANOVA (analysis of variance) model on the logarithmic scale. Thus, prior to fitting the ANOVA model, the PK parameters described in section 5.1.1 will be log transformed (natural logarithm). The difference between the expected means for log (T)-log(R) will be estimated by the difference in the corresponding Least Squares Means (point estimate).

Furthermore, the two-sided 90% confidence intervals based on the t-distribution will be computed. These quantities will then be back-transformed to the original scale to give the point estimator (geometric mean) and interval estimates for the ratio between response under test treatment and response under reference treatment.

The above mentioned ANOVA model will include effects accounting for the following sources of variation: 'subject' and 'treatment'. The effect 'subject' will be considered random, whereas the 'treatment' effect will be considered fixed. The model is described by the following equation:

 $y_{km} = \mu + s_m + \tau_k + e_{km}$, where $y_{km} = \text{logarithm of response} (AUC_{0-tz} / C_{max} \text{ for group 1 and } AUC_{0-tau} / C_{max,ss} \text{ for group 2})$ measured on subject m receiving treatment k

 μ = the overall mean,

 s_m = the effect associated with the mth subject

 τ_k = the kth treatment effect, k = 1, 2,

 e_{mk} = the random error associated with the mth subject who received treatment k.

All patients from the PKS will be included in the analysis of relative bioavailability (see Section 7.3).

As a sensitivity analysis, the model above will be fitted with the "subject" as a fixed effect.

7.3.2 Secondary endpoint analyses

The secondary PK parameters described in Section 5.1.2 will be analysed as described for the primary PK endpoints.

7.3.3 Further endpoint analyses

7.3.4 Safety analyses

All treated patients will be included in the safety analysis.

All adverse events with an onset between start and end of the residual effect period (REP), a period of 28 days after the last dose of trial medication will be assigned to the treatment period for evaluation and displayed by group (group 1 and group 2).

AEs recorded prior to intake of trial medication will be assigned to 'screening', those between first intake until the last intake of trial medication plus 28 days will be assigned to the 'on-treatment' period. Events occurring after the on-treatment period will be summarized as 'follow-up' period and those after the end of trial visit will be assigned to 'post-study' period.

Safety analyses will be descriptive in nature and will be based on BI standards. No hypothesis testing is planned.

Frequency, severity, and causal relationship of adverse events will be tabulated by system organ class and preferred term after coding according to the current version of the Medical Dictionary for Regulatory Activities (MedDRA).

Laboratory data will be analysed both quantitatively, as well as qualitatively. The latter will be done via comparison of laboratory data to their reference ranges. Values outside the reference range as well as values defined as clinically relevant will be highlighted in the listings. Laboratory data will be described with regard to distribution parameters as well as with regard to frequency and percentage of patients with abnormal values or clinically relevant abnormal values.

Vital signs, physical examinations, or other safety-relevant data observed at screening, baseline, during the course of the trial and at the end-of-trial evaluation will be assessed with regard to possible changes compared to findings before start of treatment.

7.3.5 Pharmacokinetic analyses

The pharmacokinetic parameters listed in Sections 5.1.1, 5.1.2 and 5.1.3 will be calculated according to the relevant BI internal procedures.

Only concentration values within the validated concentration range and actual sampling times will be used for the calculation of pharmacokinetic parameters. Concentrations used in the pharmacokinetic calculations will be in the same format provided in the bioanalytical report, (that is, to the same number of decimal places provided in the bioanalytical report).

The PKS will be used for the primary and secondary endpoint analyses.

The following descriptive statistics will be calculated for plasma concentrations and PK parameters: number (N), arithmetic mean, standard deviation, minimum, median, maximum, arithmetic coefficient of variation, geometric mean, and geometric coefficient of variation. The exception to this is the where only median, minimum and maximum will be calculated. The data format for descriptive statistics of concentrations will be identical with the data format of the respective concentrations. Thereafter, the individual values, as well as the descriptive statistics, will be reported with three significant digits in the clinical trial report.

For handling of missing data, please refer to Section 7.5.

Analyses will be carried out using Phoenix® WinNonlin® 6.3 (or later) and/or SAS® software, version 9.4 (or later).

7.3.6 Biomarker analyses

7.4 INTERIM ANALYSES

Interim analysis will be performed if required by the regulatory agencies.

7.5 HANDLING OF MISSING DATA

7.5.1 Safety

For partial or missing AE onset and/or end dates, BI internal rules will be followed for imputation (see Reference Document 001-MCG-156_RD01 "Handling of missing and incomplete AE dates").

7.5.2 Plasma concentration - time profiles

Concentration data identified with NOS (no sample), NOR (no valid result), NOA (not analyzed), and BLQ (below the limit of quantification) will be ignored and not replaced by zero at any time point (applies also to the lag phase). Descriptive statistics of concentrations at specific time points will be calculated only when at least 2/3 of the individuals have concentrations within the validated concentration range. The overall sample size to decide

whether the "2/3 rule" is fulfilled will be based on the total number of samples intended to be drawn for that time point (i.e. BLQ, NOR, NOS, NOA are included).

7.5.3 Pharmacokinetic parameters

In the non-compartmental analysis, concentration data identified with NOS, NOR, and NOA will not be considered. BLQ values in the lag phase will be set to zero. The lag phase is defined as the period between time zero and the first time point with a concentration above the quantification limit. All other BLQ values of the profile will be ignored. Every effort will be made to include all concentration data in an analysis. If not possible, a case-to-case decision is required whether the value should only be excluded from half-life estimation or the complete analysis.

- If a concentration is only excluded from half-life determination, it will be used for all other calculations (e.g. descriptive statistics) and for graphical presentation.
- If a concentration value is excluded from all calculations, it will not be presented graphically or used for the calculation of descriptive statistics and parameter determination. However, the excluded concentration itself will be listed in the tables in section 15 of the clinical trial report associated with an appropriate flag.

Descriptive statistics of parameters are calculated only when at least 2/3 of the individual parameter estimates of a certain parameter are available. If the actual sampling time is not recorded or is missing for a certain time point, the planned time will generally be used for this time point instead. Pharmacokinetic parameters which cannot be determined will be identified by "not calculated" (NC).

7.6 RANDOMISATION

Not applicable.

7.7 DETERMINATION OF SAMPLE SIZE

The primary endpoints for this study upon which sample size calculations have been based are AUC0-tz and Cmax of nintedanib for group 1 and AUC τ ,ss and Cmax,ss of pirfenidone for group 2.

It is planned to have at least a total of 12 patients with both evaluable PK assessments (see Section 7.3) per group in the trial, because this sample size is considered sufficient to achieve the aims of this exploratory trial. With this sample size, the following precision in estimating the ratio of geometric means (test/reference; T/R) can be expected with 95% probability. Precision is defined as the ratio of upper confidence interval limit to the relative BA estimate for both groups. Note that the precision is independent of the actual ratio of geometric means.

In the case that less than 12 patients have both PK assessments, the Trial Clinical Monitor together with the Trial Pharmacokineticist and the Trial Statistician will decide if and how many patients will be additionally included.

Page 67 of 118

Proprietary confidential information © 2016 Boehringer Ingelheim International GmbH or one or more of its affiliated companies

The observed intra-individual geometric coefficient of variation (gCV) for nintedanib in previous trials in healthy volunteers (U13-1925-01; U13-1478-01) was roughly 30% for C_{max} and 20% for AUC_{0-tz}.

For three assumptions on the intra-individual gCV of nintedanib (taking into account that the variability will be higher in patients than in healthy volunteers), Table 7.7: 1 provides an overview of the achievable precision for estimating the ratio of geometric means (T/R) for nintedanib. For illustrative purposes, the expected 90% confidence intervals with 95% coverage probability are displayed for different values of the ratios T/R of geometric means.

Table 7.7:1 Precision and illustrative two-sided 90% confidence intervals around the ratios of geometric means (T/R) for different intra-individual gCVs and ratios (T/R) in a fixed design trial (N=12)

Intra-individual gCV [%]	Ratio ¹ [%]	Precision upper CL/Ratio	90% CI [%]
30	100	1.33	75 – 133
	110	1.33	82 - 147
35	100	1.40	72 - 140
	110	1.40	79 – 153
40	100	1.42	69 - 146
	110	1.42	75 - 161

1) Ratio of the geometric means (test/reference) for a PK endpoint defined by $exp(\mu T)/exp(\mu R)$

The expected 90% confidence interval limits in the table were derived by

*CI limit*_{upper,lower} = $\exp(\ln(\theta) \pm \omega)$,

with θ being the ratio (T/R) on original scale and ω the distance from the estimate θ to either confidence interval limit on the log-scale.

Accounting for up to 4 dropouts (around 25%), a total of 16 patients (12 + 4) will be entered in the trial.

The observed total gCV in a previous parallel group trial in patients (c01787180-03) was roughly up to 40% for $C_{max,ss}$ and 40% for AUC_{$\tau,ss}$ for pirfenidone, whereby the most relevant scenarios in this trial yielded total gCVs of up to 31% for both parameters. The corresponding intra-individual gCVs can be estimated based on an assumption on the correlation between two responses of the same subject.

For three assumptions on the total gCV of pirfenidone, and assuming a ratio T/R of geometric means of 100%, Table 7.7: 2 provides an overview of the achievable precision for estimating the ratio of geometric means (T/R) for pirfenidone. For illustrative purposes, the expected 90% confidence intervals with 95% coverage probability are displayed for different values of the correlation between two responses of the same subject.

Boehringer Ingelheim 29 July 2016 BI Trial No.: 1199.229 c03463451-08 **Trial Protocol Version 4.0** Page 68 of 118

Proprietary confidential information © 2016 Boehringer Ingelheim International GmbH or one or more of its affiliated companies

Precision and illustrative two-sided 90% confidence intervals around the ratios of Table 7.7:2 geometric means (T/R; assumed to be 100%) for different total gCVs and intro-subject correlations in a fixed sequence design trial (N=12)

Total gCV [%]	Correlation	Intra-individual gCV [%]	Precision upper CL/Ratio ¹	90% CI [%]
30	0.5	21	1.23	82 - 123
	0.7	16	1.17	85 - 117
35	0.5	24	1.27	79 - 127
	0.7	19	1.19	83 - 120
40	0.5	28	1.31	77 – 131
	0.7	21	1.21	81 - 123

1) Ratio of the geometric means (test/reference) for a PK endpoint defined by $exp(\mu_T)/exp(\mu_R)$

Accounting for up to 6 dropouts (around 30%), a total of 18 patients (12 + 6) will be entered in the trial.

For these calculations the MOC3 routine from commercial software nQuery Advisor® 7.0 (Statistical Solutions, Ltd., Cork, Ireland (R15-1331) was used.

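### The precision column in Protocol Tables 7.7:1 and 7.7:2 is wrong for three of nine scenarios, each time making 12 patients look more precise than they are

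*Protocol*

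**What the plan says.** Protocol Section 7.2 states that nothing is tested in a confirmatory sense, so there is no power calculation. Section 7.7 argues from precision instead. The target is 12 pairs per group: "It is planned to have at least a total of 12 patients with both evaluable PK assessments". With that number, "the following precision in estimating the ratio of geometric means (test/reference; T/R) can be expected with 95% probability". The definition follows: "Precision is defined as the ratio of upper confidence interval limit to the relative BA estimate for both groups". The protocol adds: "Note that the precision is independent of the actual ratio of geometric means".

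The interval limits come from adding and subtracting ω on the log scale around the ratio θ, where ω is "the distance from the estimate θ to either confidence interval limit on the log-scale". Table 7.7:1 covers nintedanib at three intra-individual gCVs, each at ratios of 100% and 110%. Table 7.7:2 covers pirfenidone at three total gCVs, each at two within-subject correlations, with the ratio fixed at 100%. That makes nine variability scenarios. The first gCV 40% row of Table 7.7:1 reads "40 100 1.42 69 - 146" (gCV, ratio, precision, interval).

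**The concern.** Dividing the upper limit by the ratio has to return the precision printed in the same row, and a change in the ratio cannot alter it. Three scenarios fail this check. A further sign of trouble is in Table 7.7:2: two rows are both listed at an intra-individual gCV of 21% and both have an upper limit of 123, yet one prints 1.23 and the other 1.21.

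These tables are the only quantitative support for 12 patients per group. The protocol also expects variability in patients to exceed the healthy-volunteer values (roughly 30% for Cmax and 20% for AUC0-tz of nintedanib). The 40% row is therefore the least favourable nintedanib case shown, and it carries the largest absolute error. If the printed figures are too small, the statement that they are reached with 95% probability is false for those cells.

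**Working it through.** **Step 1. Check within the tables, with no model.** Precision = upper limit / ratio.

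- Table 7.7:1, gCV 40%, ratio 100: 146/100 = 1.46. Printed 1.42.
- Table 7.7:1, gCV 40%, ratio 110: 161/110 = 1.46. Printed 1.42.
- Table 7.7:2, total gCV 35%, correlation 0.7: 120/100 = 1.20. Printed 1.19.
- Table 7.7:2, total gCV 40%, correlation 0.7: 123/100 = 1.23. Printed 1.21.

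Conversely, a precision of 1.42 would imply intervals of 70–142 around 100 and 77–156 around 110, not the printed 69–146 and 75–161.

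**Step 2. Recompute, to find which column is wrong.** The inputs are N = 12 pairs (Section 7.7), a two-sided 90% interval from the t-distribution (Section 7.3.1: "the two-sided 90% confidence intervals based on the t-distribution will be computed") and 95% probability of achieving the width (Section 7.7). For paired data with df = 11:

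ω = t(0.95, 11) × σ_w × √(2/12) × √(χ²(0.95, 11)/11), and precision = exp(ω).

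With t = 1.796 and χ² = 19.675, the multiplier of σ_w is 1.796 × 0.4082 × 1.337 ≈ 0.9805.

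For Table 7.7:1, σ_w² = ln(1 + gCV²). For Table 7.7:2, σ_w² = (1 − ρ) × ln(1 + gCV_total²). The protocol does not write out the second formula. It gives intra-individual gCVs of 21, 16, 24, 19, 28 and 21%, which are exactly the six printed in the table.

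Worked case, gCV 40%: σ_w = √ln(1.16) = 0.3853; ω = 0.9805 × 0.3853 = 0.3778; exp(ω) = 1.459.

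| Scenario | Recomputed | Printed |
|---|---|---|
| Table 7.7:1, 30% | 1.334 | 1.33 |
| Table 7.7:1, 35% | 1.396 | 1.40 |
| **Table 7.7:1, 40%** | **1.459** | **1.42** |
| Table 7.7:2, 30%, ρ 0.5 | 1.226 | 1.23 |
| Table 7.7:2, 30%, ρ 0.7 | 1.171 | 1.17 |
| Table 7.7:2, 35%, ρ 0.5 | 1.266 | 1.27 |
| **Table 7.7:2, 35%, ρ 0.7** | **1.200** | **1.19** |
| Table 7.7:2, 40%, ρ 0.5 | 1.306 | 1.31 |
| **Table 7.7:2, 40%, ρ 0.7** | **1.230** | **1.21** |

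Six scenarios reproduce to two decimals and three do not. The intervals printed beside the three failures do reproduce: 68.5–145.9, 83.3–120.0 and 81.3–123.0.

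**Step 3. Size.** Comparing ln(printed) with ω:

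- ln(1.42)/0.3778 = 0.928, so the half-width is understated by 7%.
- ln(1.19)/0.1826 = 0.953, understated by 5%.
- ln(1.21)/0.2069 = 0.921, understated by 8%.

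At N = 12 a precision of 1.42 corresponds to an intra-individual gCV of 37%. At gCV 40%, 13 pairs give 1.428 and 14 give 1.402.

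**Step 4. Could another reading explain the printed values?** Variants tried at N = 12 included conditioning on the interval covering the true ratio, using the rounded intra-individual gCVs, a normal instead of a t quantile, and expected width with no probability statement. None gives all three printed values at 95% probability. Conditioning on coverage gives 1.463, 1.202 and 1.232, which round to the same corrected figures. Replacing 95% by 90% probability gives 1.425, 1.187 and 1.214, which match the three printed values to two decimals. The other six cells would then be 1.31, 1.37, 1.21, 1.16, 1.25 and 1.28, and none of these matches. A wrong setting for these cells is therefore a plausible cause, but that is inference.

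**The case against.** The case for treating this as editorial has substance. The correct interval stands beside every faulty figure, and the precision column only restates it, so a careful reader is not misled about the width. Section 7.7 calls 12 patients sufficient for an exploratory trial and sets no precision threshold. The enrolment figures of 16 and 18 come from dropout allowances. The final intervals will use the observed variability, whatever these tables say. All of this stands. It means that 14 pairs is a way of expressing the size of the error and not a shortfall against a requirement.

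Three further points also stand:

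- The nintedanib 40% row is the worst only in absolute units (0.04). On the log scale the pirfenidone 40%/0.7 row is slightly worse.
- The 1.19 against 1.20 discrepancy is only 0.01.
- The interval column is not perfect. At ratio 110 the recomputed upper limits are 153.5 (printed 153) and 160.5 (printed 161). These are differences of a rounding unit and do not affect the ratio-100 rows on which the argument rests.

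None of this makes the printed precision values correct. Rounding cannot turn 1.459 into 1.42 or 1.230 into 1.21.

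**Conclusion.** The concern holds. Three of nine scenarios (four cells, because 1.42 appears twice) contradict both the protocol's definition of precision and the intervals in their own rows. The correct values are 1.46, 1.20 and 1.23. All three errors make the design look better than it is, by 5% to 8% of the log half-width. At the stated variabilities the printed values would be achieved with about 89% (1.42), 92% (1.19) and 88% (1.21) probability, not 95%.

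The contradiction in Step 1 needs no assumption beyond the protocol's definition. Identifying the precision column as the faulty one rests on the standard paired t-interval calculation, which reproduces the other six scenarios. The correction should be made because these are the only numbers offered in support of the sample size. It does not call into question the sample size, the endpoints or the analysis model.

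**What to change.** In Protocol Section 7.7, change the precision column as follows:

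- Table 7.7:1, gCV 40%: 1.42 becomes 1.46 in both ratio rows.
- Table 7.7:2, total gCV 35%, correlation 0.7: 1.19 becomes 1.20.
- Table 7.7:2, total gCV 40%, correlation 0.7: 1.21 becomes 1.23.

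Keep 12 evaluable patients per group, and use the corrected figures wherever planned precision is later cited, for example in the trial report. The SAP refers to the protocol for sample size planning and repeats none of these values, so it needs no edit. The cost is four table cells and a slightly less favourable statement of precision; enrolment does not change.

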8. INFORMED CONSENT, DATA PROTECTION, TRIAL RECORDS

The trial will be carried out in accordance with the Medical Devices Directive (93/42/EEC) and the harmonized standards for Medical Devices (ISO 14155-01 and ISO 14155-02).

The trial will be carried out in compliance with the protocol, the ethical principles laid down in the Declaration of Helsinki, in accordance with the ICH Harmonized Tripartite Guideline for Good Clinical Practice (GCP), relevant BI Standard Operating Procedures (SOPs), and relevant regulations*.

Standard medical care (prophylactic, diagnostic and therapeutic procedures) remains in the responsibility of the treating physician of the patient.

The Investigator will inform the Sponsor immediately of any urgent safety measures taken to protect the trial subjects against any immediate hazard, and also of any serious breaches of the protocol or of ICH GCP*.

The rights of the Investigator and of the Sponsor with regard to publication of the results of this trial are described in the Investigator contract. As a rule, no trial results should be published prior to finalization of the Clinical Trial Report.

The rights of the investigator / trial site and of the sponsor with regard to publication of the results of this trial are described in the investigator contract / trial site's contract. As a general rule, no trial results should be published prior to finalisation of the Clinical Trial Report. The certificate of insurance cover is made available to the Investigator and the patients, and is stored in the ISF (Investigator Site File)."

8.1 TRIAL APPROVAL, PATIENT INFORMATION, AND INFORMED CONSENT

This trial will be initiated only after all required legal documentation has been reviewed and approved by the respective Institutional Review Board (IRB) / Independent Ethics Committee (IEC) and competent authority (CA) according to national and international regulations. The same applies for the implementation of changes introduced by amendments.

Prior to patient participation in the trial, written informed consent must be obtained from each patient (or the patient's legally accepted representative) according to ICH / GCP and to the regulatory and legal requirements of the participating country. Each signature must be personally dated by each signatory and the informed consent and any additional patient-information form retained by the Investigator as part of the trial records. A signed copy of the informed consent and any additional patient information must be given to each patient or the patient's legally accepted representative."

8.2 DATA QUALITY ASSURANCE

A quality assurance audit/inspection of this trial may be conducted by the Sponsor, Sponsor's designees, or by IRB / IEC or by regulatory authorities. The quality assurance auditor will have access to all medical records, the Investigator's trial-related files and correspondence, and the informed consent documentation of this clinical trial.

8.3 RECORDS

Case Report Forms eCRF for individual patients will be provided by the Sponsor. See Section 4.1.5.2 for rules about emergency code breaks. For drug accountability, refer to Section 4.1.8.

8.3.1 Source documents

Source documents provide evidence for the existence of the patient and substantiate the integrity of the data collected. Source documents are filed at the Investigator's site.

Data reported on the CRF must be consistent with the source data or the discrepancies must be explained. The Investigator may need to request previous medical records or transfer records, depending on the trial; current medical records must also be available. For eCRFs all data must be derived from source documents.

